## 8.0 Subject Numbers and Statistical Plan

### 8.1 Number of Subjects

Ten (10) subjects will be enrolled in the study.

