## 2.3

### Study Rationale

Both ketoconazole and posaconazole are FDA-approved anti-fungal agents with a well-established side effect and safety profile. Ketoconazole and posaconazole have shown efficacy in reducing tumor cell proliferation in our *in vitro* studies. Furthermore, both have also shown efficacy, mediated at least in part through inhibition of HK2 activity, in our animal models with dosing concentration and schedules that are documented as safe in humans.[58] As a drug, posaconazole has a more predictable half-life than ketoconazole and has less off-target effects. Therefore, the proposed trial will focus on the role of posaconazole exclusively. As a first step, demonstration of adequate penetrance of study drug in brain and tumor tissue (pharmacokinetics) and biological effect (inhibition of glycolysis and subsequent tumor cell death) is necessary prior to large scale clinical studies. A total of 5 control participants will be included in this study as we specifically want to assess for pharmacodynamic differences too. The

addition of a control group to this study rather to both the studies (ketoconazole study is a separate protocol) is because we feel posaconazole may be a more promising drug for moving forward.

Plasma drug concentration measurements are an unreliable method to assess delivery of drugs across the blood-brain barrier. In contrast, intracerebral MDC monitoring allows for approximate measurements within extracellular fluid (ECF) sampling of the brain. MDC placement within the brain is not a novel technique and has been utilized routinely in the ICU setting to measure brain metabolism by sampling of ECF of traumatic brain injury patients [59-61].

MDC are now FDA-approved and are being placed routinely with intracranial pressure monitors. This method allows for continuous measurement of ECF within a tumor or normal tissue. The dialysis probe has a semipermeable membrane which is less than 1 mm in diameter into which two sections of microcatheter are fused. Previous studies have demonstrated the feasibility of keeping the catheters in place of critically injured patients for up to 2 weeks [62-64].

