## **7.0 Study Design and Procedures**

### **7.1 Study Design**

[figure not shown]
This will be a single-center, open label, non-randomized Phase 0 feasibility trial to determine the neuro-pharmacokinetic/pharmacodynamic profile of posaconazole for HGGs. We will enroll 10 (5 for study group and 5 for control group) evaluable patients over 12 months with recent MRI findings suggestive of

high grade gliomas with need for surgical resection. Our historical surgical volume supports the feasibility of this proposal.

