### 8.2 Sample size determination

#### Design

This is an exploratory (pilot) study to assess whether posaconazole can penetrate brain tissue at sufficient enough levels to result in expected downstream biological effects on glycolysis and tumor cell survival. Five evaluable patients will be studied for this trial. The sample size justification is not based on statistical rationale but clinical affordability.

The following metrics will be used to define success and support the decision to proceed with advanced phase trials:

- Detection of  $\geq 5\mu\text{M}$  concentration of either drug in resected tumor in at least 2 of 5 patients in each arm – a value that is within the range needed to achieve efficacy for CNS fungal infections and to achieve 50% glioma tumor cell kill *in vitro* based on our prior published report (ref 58); AND
- Reduction in average lactate and pyruvate concentrations in both resected tumor and dialysate fluid (using MDCs) in the treated cohorts compared to controls; AND
- Steady concentration of lactate and pyruvate over 24 hours of monitoring with MDCs in control participants.

The rationale for the above is based on the notion that any tumor penetration by drug, with concomitant effect on glycolysis, warrants further in-depth analysis as our therapeutic options for these deadly tumors are currently very limited. Intra-tumoral drug concentration on the lower range would still be promising and warrant dose-escalation studies, as the currently selected dosing is based on anti-fungal regimens that are known to be safe. Phase II studies for assessing tumor response would be warranted if substantial tumor penetration together with expected biological effect is observed. A negative trial would nonetheless have value as it would serve as an efficient means of determining whether or not either of ketoconazole or posaconazole hold promise against GBMs, as part of a “fail early” approach to drug-development, while minimizing the human and financial cost investment.

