### **Study Population**

Only patients who are eligible and take posaconazole according to protocol specifications (study drug arm only) **and** have undergone successful MDC implantation will be considered evaluable and included in the study analysis. Otherwise, enrolled patients will be replaced. All eligible patients for whom analyzable dialysate samples were obtained for at least 7 of the 9 time points will be considered evaluable for the primary study endpoint. Patients who are not evaluable will be replaced.

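### Section 8.1 counts ten subjects enrolled, 7.1 counts ten evaluable, and 8.2 requires non-evaluable patients to be replaced; these agree only if no enrolled patient is lost

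*Combined protocol and SAP*

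**What the plan says.** The size of the trial is stated in several places, in different units.

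- Section 8.1: "Ten (10) subjects will be enrolled in the study". There is no qualifier and no maximum.
- Section 7.1: "We will enroll 10 (5 for study group and 5 for control group) evaluable patients over 12 months".
- Section 8.2, Design: "Five evaluable patients will be studied for this trial". No arm is named. The basis is given as "The sample size justification is not based on statistical rationale but clinical affordability".
- Section 2.3, Study Rationale: "A total of 5 control participants will be included in this study".
- Section 15.2 rates recruitment of ten subjects as likely to succeed and makes no allowance for losses.

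Replacement is also described in more than one way.

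- Section 8.2, Study Population, limits the analysis to eligible patients with successful catheter implantation and, in the drug arm, posaconazole taken per protocol. It adds "Otherwise, enrolled patients will be replaced". It then sets a sampling threshold in these words: "analyzable dialysate samples were obtained for at least 7 of the 9 time points will be considered evaluable for the primary study endpoint". The paragraph ends on a second replacement rule, worded without any ceiling: "Patients who are not evaluable will be replaced".
- Section 3.3.2 makes replacement optional, and only for patients who stop treatment for reasons other than an adverse event or unacceptable toxicity.
- Sections 7.2 and 7.2.1 turn a patient away from the control arm once five participants have been enrolled in it. The count is of enrolled, not evaluable, participants.

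**The concern.** Enrolled and evaluable are different counts here, because the protocol foresees losses between the two. Under 7.2.4, a malpositioned catheter or significant bleeding in the tumour bed cancels the microdialysis. Under 8.2, a drug-arm patient who does not take posaconazole as specified is not evaluable, and a patient in either arm with fewer than 7 of 9 usable dialysate samples is not evaluable for the primary endpoint. The off-study criteria in 8.3 add patients who miss more than three doses.

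Once one enrolled patient is lost in any of these ways, the study team cannot follow all the text. Stopping at ten enrolled satisfies 8.1 but misses the 7.1 target and the replacement rule in 8.2. Replacing the patient satisfies 7.1 and 8.2 but takes enrolment past the figure in 8.1. If the lost patient is a control, the cap in 7.2 and 7.2.1 bars the replacement that 8.2 requires.

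Two things are at stake: the number of patients behind the primary descriptive summary, and the number of people exposed to study drug or a research brain catheter in a trial that, by section 11.1, offers participants no direct benefit. Because the size rests on affordability, the real enrolment figure also bears on the budget.

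**Working it through.** **The plan's own figure.** 5 study drug + 5 control = 10, so the total in 7.1 is reproduced. Sections 8.1 and 7.1 give the same number but count different things. No alpha, power, effect size or standard deviation is given, so there is no power calculation to check.

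**When the statements agree.** Let q be the chance that an enrolled patient is evaluable. Ten enrolled equals ten evaluable with certainty only when q = 1.

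**Assumption.** The documents give no evaluable rate. The values of q below are assumptions, spanning 95% to 70%. They treat patients as independent and use one rate for both arms. That is a simplification, since the drug-compliance condition applies only to the drug arm.

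**Formulas.**

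- Chance that all ten enrolled are evaluable: q^10. At q = 0.90, 0.90^10 = 0.349.
- Expected evaluable among ten enrolled: 10q.
- Expected enrolment when replacing until ten are evaluable: 10/q. At q = 0.80, 10/0.80 = 12.5.
- Per-arm inflation: 5/q, rounded up within each arm. At q = 0.80, 5/0.80 = 6.25, so 7 per arm and 14 in total.
- Planning ceiling: the smallest n per arm for which P(Bin(n, q) ≥ 5)² ≥ 0.90, so that both arms reach five with at least 90% probability.

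| Assumed q | q^10 | Expected evaluable of 10 | Expected enrolment for 10 evaluable | 5/q rounded up, both arms | Total for 90% chance of five in each arm |
|---|---|---|---|---|---|
| 0.95 | 0.599 | 9.5 | 10.5 | 6 + 6 = 12 | 6 + 6 = 12 |
| 0.90 | 0.349 | 9.0 | 11.1 | 6 + 6 = 12 | 7 + 7 = 14 |
| 0.80 | 0.107 | 8.0 | 12.5 | 7 + 7 = 14 | 9 + 9 = 18 |
| 0.70 | 0.028 | 7.0 | 14.3 | 8 + 8 = 16 | 10 + 10 = 20 |

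The per-arm columns exceed 10/q because the target is five in each group, not ten in any split.

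**Control arm alone.** Under the cap of five enrolled, the chance that all five controls are evaluable is q^5: 0.774, 0.590, 0.328 and 0.168 at the four rates. The complement is the chance that 8.2 calls for a replacement that 7.2 forbids: 23%, 41%, 67% and 83%.

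**Replacement rules side by side.** Section 8.2: mandatory, whatever the cause of non-evaluability, no ceiling. Section 3.3.2: optional, with adverse-event and toxicity withdrawals outside its scope. A drug-arm patient who stops for toxicity before surgery, and so has not taken drug as specified, must be replaced under 8.2 but is not covered by 3.3.2.

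**The case against.** The best defence is that 8.1 is shorthand. Section 7.1 says what the ten are, 8.2 provides for replacement, and nothing calls ten a maximum. Read together, enrolment simply continues until ten are evaluable. That reading is reasonable for 8.1 alone, but it does not resolve the control-arm cap, which is expressly counted on enrolled participants, or the different rule in 3.3.2. It also leaves the trial with no stated upper limit.

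Four stronger readings are tempting, and the documents do not support them.

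- *Ten enrolled cannot deliver ten evaluable.* They can, if every patient is evaluable. The statements fail only when someone is lost.
- *Section 8.2 also demands ten evaluable.* It says five. The sentence follows one about posaconazole penetration, and controls are described separately in 2.3, so it may well mean the drug arm only. The defect is that the arm is not named.
- *The 2-of-5 success rule loses its denominator.* That rule concerns drug in resected tumour, which is sampled before the catheter is placed, whereas the 7-of-9 criterion governs evaluability for the dialysate endpoint. Failing 7 of 9 does not clearly remove a patient from the tumour rule. The catheter-implantation condition in 8.2 might, but the text does not say how the two interact.
- *Every replacement means another person given both drug and catheter.* Patients without high-grade glioma at surgery are classed as screen failures in 7.2.3 and receive no catheter, though those in the drug arm will already have taken drug. Replacement controls receive no drug.

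It is also fair to say that the probabilities rest on assumed rates, that the analysis is descriptive, and that 8.3 already plans a summary of patient disposition.

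**Conclusion.** The point holds: wrong as written, with modest impact. Ten enrolled (8.1), ten evaluable (7.1) and mandatory replacement (8.2) are compatible only with zero loss after enrolment. The control-arm cap in 7.2 and 7.2.1 contradicts the 8.2 replacement rule as soon as one of five enrolled controls is non-evaluable. Section 3.3.2 does not match 8.2, and the figure of five in 8.2 needs an arm.

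How often this would bite depends on an evaluable rate that the documents do not give. Even at an assumed 95%, ten enrolled yield ten evaluable only about 60% of the time; at 70% the figure is 3%. Expected enrolment for ten evaluable runs from 10.5 to 14.3 over that range, roughly one to four patients beyond the figure in 8.1.

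No type I error or power claim is affected, because none is made. The consequence is an undefined enrolment limit and, possibly, fewer than five patients in a descriptive summary.

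**What to change.** One amendment to the wording, leaving the evaluable target in 7.1 unchanged:

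1. Restate 8.1 as ten evaluable patients (five per group), up to N enrolled. Take N from the sponsor's own expected evaluable rate, and state that rate. As illustrations only, rounding 5/q up within each arm gives 12 at 90% and 14 at 80%; a 90% chance of reaching five in both arms needs 14 and 18.
2. In 8.2, name the arm or arms to which the five evaluable patients belong.
3. In 7.2 and 7.2.1, count the control-arm cap on evaluable participants, subject to the overall maximum.
4. Reconcile 3.3.2 with 8.2 so that one replacement rule applies, and say whether adverse-event withdrawals are replaced.
5. Bring the feasibility statement in 15.2 into line with N.
6. Add to the disposition summary in 8.3 the numbers enrolled, exposed to drug, implanted with a catheter and evaluable, separately by arm.

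The cost is a protocol amendment and, if N exceeds ten, a matching update of the budget. No assay, visit or analysis method changes.

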### 8.2 Sample size determination

#### Design

This is an exploratory (pilot) study to assess whether posaconazole can penetrate brain tissue at sufficient enough levels to result in expected downstream biological effects on glycolysis and tumor cell survival. Five evaluable patients will be studied for this trial. The sample size justification is not based on statistical rationale but clinical affordability.

The following metrics will be used to define success and support the decision to proceed with advanced phase trials:

- Detection of  $\geq 5\mu\text{M}$  concentration of either drug in resected tumor in at least 2 of 5 patients in each arm – a value that is within the range needed to achieve efficacy for CNS fungal infections and to achieve 50% glioma tumor cell kill *in vitro* based on our prior published report (ref 58); AND
- Reduction in average lactate and pyruvate concentrations in both resected tumor and dialysate fluid (using MDCs) in the treated cohorts compared to controls; AND
- Steady concentration of lactate and pyruvate over 24 hours of monitoring with MDCs in control participants.

The rationale for the above is based on the notion that any tumor penetration by drug, with concomitant effect on glycolysis, warrants further in-depth analysis as our therapeutic options for these deadly tumors are currently very limited. Intra-tumoral drug concentration on the lower range would still be promising and warrant dose-escalation studies, as the currently selected dosing is based on anti-fungal regimens that are known to be safe. Phase II studies for assessing tumor response would be warranted if substantial tumor penetration together with expected biological effect is observed. A negative trial would nonetheless have value as it would serve as an efficient means of determining whether or not either of ketoconazole or posaconazole hold promise against GBMs, as part of a “fail early” approach to drug-development, while minimizing the human and financial cost investment.

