### **Control group**

Participants will first be considered for enrolment in the posaconazole arm. If there are contraindications to posaconazole, or if enrolment in posaconazole arm has been completed, then subjects will be enrolled in the ketoconazole study, which has a separate IRB-approved protocol (IRB# STUDY00014115). If enrollment in the ketoconazole study is already completed or if the participant is not a candidate for ketoconazole either, then they will be considered for possible candidacy in the control arm.

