#### **Intra-operative procedure**

##### **Assessments common to both control and study drug groups**

After surgical resection, frozen pathology will be reviewed to verify the diagnosis of HGG. Once pathology has been verified, and it is determined there is adequate tissue for clinical diagnosis, we will take our research sample will be taken and prepared for assessment of intra-tumoral drug concentration (study drug arm only) and assessment of HK2 activity, downstream glycolysis metabolites, tumor cell proliferation, and angiogenesis.

Where an open surgical resection has been planned, one (1) tissue sample will be from the center of the tumor and one (1) from the tumor capsule and snap-frozen immediately in the operating room (<15 minutes). No individual sample will be greater than 1cm x 1cm. These will then be divided for individual research-specific analyses.

As noted below for postoperative plasma collection schedule, blood samples will be obtained at the time of tumor sampling as well to determine and compare tumor: blood drug concentration ratios. The exact time of tumor resection and blood sampling will be recorded.

For patients in whom the intraoperative diagnosis is not consistent with HGG, no additional blood will be drawn and the patient will not be able to continue study and will be considered a

screen fail. Furthermore, no MDC will be inserted. Surgical procedures necessary for the management for the particular diagnosis will be undertaken as per standard protocol for the surgeon.

Upon satisfactory resection of tumor bulk, the neurosurgeon will place two CMA 70 MDCs with Gold Tip - (ref. no. P000050, CMA, Solna, Sweden) with a membrane length of 10mm, and shaft length 100mm - in accordance with pre-op MRI. For patients with a subtotal resection of enhancing tumor, one MDC will be placed in a contrast enhancing area of the tumor and another will be placed in a non-contrast enhancing region (normal brain) within 5mm of tumor resection cavity. For patients with a complete resection of contrast-enhancing tumor, only one MDC will be placed in the non-enhancing tumor resection boundary, within 5mm of resection cavity. Ultimately, the decision on number of catheters inserted will be at the discretion of the surgeon. Upon completion of the surgical procedure, the wound will then be irrigated and closed in standard fashion and lastly the catheter will be anchored to the scalp with sutures and sterile dressings.

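### Success criterion 1 cannot be applied as written: it asks for either drug in each arm, but the protocol has one posaconazole arm and one undosed control arm

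*Combined protocol and SAP*

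**What the plan says.** Section 8.2 (Design) lists three metrics, joined by AND, that define success and inform the decision to go on to later-phase trials.

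- Criterion 1 requires at least 5 µM, stated as "concentration of either drug in resected tumor in at least 2 of 5 patients in each arm".
- Criterion 2 requires lower average lactate and pyruvate "in the treated cohorts compared to controls".
- Criterion 3 concerns control participants only.

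The section closes by saying that a negative result would still be useful for "determining whether or not either of ketoconazole or posaconazole hold promise against GBMs".

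The rest of the protocol describes one dosed group. Section 2.3 says "the proposed trial will focus on the role of posaconazole exclusively" and, in explaining the "addition of a control group to this study rather to both the studies (ketoconazole study is a separate protocol"), places ketoconazole outside this study. Section 7.1 gives the groups: "We will enroll 10 (5 for study group and 5 for control group) evaluable patients over 12 months". Under Visit 1 (Control group), patients who cannot enter the posaconazole arm are first directed elsewhere: "subjects will be enrolled in the ketoconazole study, which has a separate IRB-approved protocol". The intra-operative procedures in Section 7.2.3 limit the "assessment of intra-tumoral drug concentration (study drug arm only").

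**The concern.** Criteria 1 and 2 are worded for two dosed groups, and the protocol has one. Within it, there is no second drug for criterion 1 to refer to, and one of the two arms receives no drug and has no tumour drug assay. The rule that decides whether development continues therefore cannot be followed to the letter. Whoever applies it must first decide what it means. The study is open label, and unless the text is corrected beforehand, that decision could be made after tumour levels are known.

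**Working it through.** **No power figure to reproduce.** Section 8.2 says the size rests on affordability, not on a statistical rationale. The group sizes agree: 5 + 5 = 10, as in Sections 7.1 and 8.1.

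**Literal reading on this protocol's two arms.** Let p be the chance that a dosed patient reaches 5 µM in resected tumour, and P the chance that at least 2 of 5 do:

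P = 1 − (1−p)^5 − 5p(1−p)^4.

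In the undosed arm p = 0, so P = 0. The chance that each arm passes is P × 0 = 0 at every p. In practice the control arm would not even have a measurement to judge.

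**Reading on two azole arms.** Section 8.2 (Study Population) confines the analysis to eligible patients of this study who, in the drug arm, took posaconazole as specified and had a successful catheter placement. Ketoconazole patients are enrolled under another protocol and do not meet that definition. This reading therefore needs data from outside the analysis set.

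**Intended reading.** The opening of Section 8.2 (Design) names posaconazole alone. Section 8.3 defines the primary outcome as posaconazole AUC0-24 and compares the pharmacodynamic values with the control arm. Together with the analysis set, this points to at least 2 of 5 posaconazole patients.

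**Size, if both azole studies had to pass.** The documents give neither p nor the size of the ketoconazole study. Assumptions: 5 patients per drug, independent patients, the same p for both drugs. The both-must-pass call differs from the intended call only when posaconazole passes and ketoconazole fails, which has probability P(1−P) = P − P².

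| Assumed p | Intended: P | Both must pass: P² | Calls differ: P(1−P) |
|---|---|---|---|
| 0.2 | 0.2627 | 0.0690 | 0.2627 × 0.7373 = 0.19 |
| 0.3 | 0.4718 | 0.2226 | 0.4718 × 0.5282 = 0.25 |
| 0.5 | 0.8125 | 0.6602 | 0.8125 × 0.1875 = 0.15 |
| 0.7 | 0.9692 | 0.9394 | 0.9692 × 0.0308 = 0.03 |

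Overall success also needs criteria 2 and 3. With those read the same way in both cases, the overall call changes only if criterion 1 changes and both of the others are met. P(1−P) is therefore an upper bound on that effect.

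**Sensitivity to equal rates.** With unequal rates the difference is the intended probability minus the both-must-pass probability. For posaconazole at 0.5, it is 0.8125 − 0.0662 = 0.75 with ketoconazole at 0.1, and 0.8125 − 0.7875 = 0.03 with ketoconazole at 0.7. For posaconazole at 0.3, the corresponding figures are 0.4718 − 0.0384 = 0.43 and 0.4718 − 0.4573 = 0.01.

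**The case against.** The strongest reply is that nobody would misapply the rule. The wording looks carried over from a two-drug plan, the analysis set admits only this protocol's patients, and Section 8.3 already sets posaconazole against control for the pharmacodynamic values. The metrics only support a decision, and Section 8.2 says concentrations on the lower side would still be promising and justify dose-escalation work. The size and success rule of the ketoconazole study are not in these documents, so any joint calculation rests on assumptions.

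Most of this stands, and it limits the point to a minor one. It does not remove it. Neither the analysis-set paragraph nor Section 8.3 restates criterion 1, and the two-drug wording recurs in criterion 2 and in the closing sentence, so it is not a single slip.

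Three stronger inferences are not supported:

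- A reader might infer from the words on either drug that one azole passing is enough. Criterion 1 requires the threshold in each arm, which resists that. The closing sentence describes the value of a negative trial and is not part of the rule.
- A reader might size the problem by the chance that exactly one of two azole studies passes, 2P(1−P) = 0.39, 0.50, 0.30 and 0.06 at the four rates. That measures how often both-must-pass and either-may-pass disagree with each other. Against the intended reading, the figure is half as large.
- A reader might infer that the controls formally serve both studies. Section 2.3 explains why the control group sits here, but does not say that ketoconazole patients will be compared with it.

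**Conclusion.** Criterion 1 is wrong as written; severity is minor. On this protocol's two arms it can never be met, and on two azole arms it calls for patients outside the analysis set. The likely intent is at least 2 of 5 posaconazole patients, and under that reading there is no discrepancy in the success call. If both studies had to pass, the criterion 1 call would differ with probability about 0.19, 0.25, 0.15 or 0.03 at p = 0.2, 0.3, 0.5 or 0.7. This assumes 5 independent patients per drug and equal rates, and it bounds the effect on overall success with criteria 2 and 3 held fixed. Unequal rates can make it larger or smaller.

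A reader might infer that undosed patients are meant to reach 5 µM, or that the trial cannot succeed. The documents do not support either: they name posaconazole at the outset and treat controls as the comparison group. The 5 µM threshold is not in question here, and the primary AUC0-24 endpoint, sample size and procedures are unaffected.

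**What to change.** Make three wording changes in Section 8.2 (Design):

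1. Criterion 1: posaconazole at or above 5 µM in resected tumour in at least 2 of the 5 evaluable study drug arm patients.
2. Criterion 2: state the lactate and pyruvate comparison as the posaconazole arm against the control arm, in line with Section 8.3.
3. Closing fail-early sentence: limit it to posaconazole.

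The cost is a protocol text amendment, best made before any tumour concentrations are known. The threshold, number of patients, assays and primary endpoint stay as they are.

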### Ketoconazole and posaconazole enhance *in vitro* survival in part through down-regulation of HK2 activity

Upon identification of ketoconazole and posaconazole as potential inhibitors of HK2-regulated gene expression networks, we conducted dynamic metabolic flux analysis with C-labeling experiments followed by liquid chromatography-mass spectrometry (LC-MS) to assess the effect of the addition of ketoconazole or posaconazole, on glycolytic intermediates from GBM cell lines and Glioma stem cell cultures [58]. Through this approach, we demonstrated a reduction of various pro-anabolic glycolytic intermediates through the addition of these azoles (Figure 4A). This was shown to be at least in part due to the down-regulation of HK2 activity, and hence reduction of lactate production, by azoles (Figure 4 B, and C) Loss of HK2 in GBM cells dampened the effect of several azoles suggesting that the mechanism of action is mediated in part through HK2 (Figure 4D). The addition of ketoconazole or posaconazole (IC50 = 10  $\mu$ M) decreased the viability of several GBM cell lines (Figure 4E) and glioma stem cells (Figure 4F) but not normal human astrocytes (NHA).

[figure not shown]

Figure 4 D. Glioma cell line viability is decreased following treatment with Ketoconazole and Posaconazole. This effect on viability is decreased in the absence of HK2 (knock-down)

[figure not shown]

Figure 4E. Increasing concentrations of Ketoconazole and Posaconazole decrease the % viability of GBM cell lines but not normal human astrocytes (NHA).

[figure not shown]

Figure 4F. Increasing concentrations of ketoconazole and posaconazole decrease the viability of glioma stem cell lines but not normal stem cell lines (NSC).

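### The 5 µM tumour criterion is tied to 50% glioma cell kill in vitro, but the only IC50 the protocol quotes is 10 µM; the two statements need reconciling

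*Combined protocol and SAP*

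**What the plan says.** Section 8.2 (Design) lists three metrics, joined by AND, that define success and support moving to later-phase trials.

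- **Concentration.** Drug in resected tumour must reach at least 5 µM "in at least 2 of 5 patients in each arm". The value is described as "a value that is within the range needed to achieve efficacy for CNS fungal infections and to achieve 50% glioma tumor cell kill" in vitro, and the source is "based on our prior published report (ref 58); AND". The limits of the range are not stated.
- **Treated versus control.** Average lactate and pyruvate must be lower than in controls, in both tumour and dialysate.
- **Controls.** Lactate and pyruvate must stay steady over 24 hours of microdialysis.

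The same section then describes what would follow. Low tumour levels are not a failure: "Intra-tumoral drug concentration on the lower range would still be promising and warrant dose-escalation studies". Phase II is reserved for substantial penetration accompanied by the anticipated biological effect. Neither level is given a number.

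Section 2.2, in the subsection on in vitro survival, summarises reference 58: "The addition of ketoconazole or posaconazole (IC 50 = 10" µM) reduced the viability of several GBM lines and of glioma stem cells. That one value covers both drugs. The dose-response data by cell line are in Figures 4E and 4F, which are not reproduced in the text available for this review.

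**The concern.** An IC50 is the concentration giving 50% of the effect. Sections 2.2 and 8.2 rest on the same report, yet the cut-off linked to 50% kill is half the one 50% concentration that the protocol states. Nothing in the text puts 50% kill at 5 µM.

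The cell-kill statement is also the only part of the justification that connects 5 µM to tumour cell survival, which Section 8.2 names as part of the question. The antifungal justification carries no figure and concerns a different effect.

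What is at stake is how a result between 5 and 10 µM is read. As written, it could be reported as reaching a 50%-kill concentration, although the protocol's only quoted value says otherwise. Because low and substantial penetration have no numbers, the same result could be assigned to dose escalation or to Phase II after the data are seen.

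**Working it through.** Section 8.2 offers no calculation for 5 µM and says the sample size has no statistical basis, so there is no plan figure to reproduce. The check compares the two concentrations and then asks how much the choice of cut-off matters.

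**Inputs from the documents:** cut-off 5 µM and the 2-of-5 rule (Section 8.2); IC50 10 µM (Section 2.2); molecular weight 700.8 (Section 7.4.1).

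**Step 1. Ratio.** 5/10 = 0.5. In mass units, 5 × 700.8/1000 = 3.50 µg/mL against 10 × 700.8/1000 = 7.01 µg/mL.

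**Step 2. Predicted kill at 5 µM if the IC50 is 10 µM.** Assume a Hill curve with 100% maximum effect:

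kill = C^h/(C^h + IC50^h) = 1/(1 + 2^h) at C = 5 µM.

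The slope h is not in the documents, so a range is shown.

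| Assumed h | Kill at 5 µM |
|---|---|
| 0.5 | 41% |
| 1 | 33% |
| 1.5 | 26% |
| 2 | 20% |
| 3 | 11% |

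Since 2^h exceeds 1 for any positive h, kill is below 50% whatever the slope. How far below depends entirely on the assumed slope.

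**Step 3. Chance of meeting the concentration metric.** If each patient exceeds the cut-off with probability p, then

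P(at least 2 of 5) = 1 − (1 − p)^5 − 5p(1 − p)^4.

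At p = 0.5 this is 1 − 0.03125 − 0.15625 = 0.8125. For illustration, take tumour levels as log-normal with σ = √ln(1 + CV²) and p = 1 − Φ(ln(cut-off/median)/σ). Medians and CVs are assumptions.

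| Assumed median | CV | P at 5 µM cut-off | P at 10 µM cut-off |
|---|---|---|---|
| 5 µM | 40% | 0.81 | 0.01 |
| 5 µM | 60% | 0.81 | 0.09 |
| 5 µM | 100% | 0.81 | 0.27 |
| 7.5 µM | 40% | 1.00 | 0.32 |
| 7.5 µM | 60% | 0.99 | 0.48 |
| 7.5 µM | 100% | 0.96 | 0.60 |
| 10 µM | 40% | 1.00 | 0.81 |
| 10 µM | 60% | 1.00 | 0.81 |
| 10 µM | 100% | 0.99 | 0.81 |

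So if typical tumour levels lie at or somewhat above 5 µM, the cut-off largely decides whether this metric is met. These are probabilities for the concentration metric only, not for the full three-part rule.

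**The case against.** The strongest reply is that Section 8.2 says 5 µM lies within a range; it does not say that 5 µM gives 50% kill. A single figure covering two drugs, several GBM lines and stem-cell cultures reads as a summary, and individual lines may well have IC50 values near 5 µM. The per-line data are in figures and a report not available here. This stands: the mismatch is apparent, not a proven error. It does not remove the need to state the range, because the one value in the text does not support the claim.

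A reader might go further and infer that a go can be declared at half the level the protocol's own data require. The documents do not support that, for two reasons.

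- The concentration metric cannot produce a go alone. Both lactate and pyruvate conditions must also hold, so glycolytic effect is measured in patients and not inferred from 5 µM.
- Nowhere does the plan require the IC50 to be reached. Its rationale is that any entry of drug into tumour, if glycolysis is also affected, justifies further study, and it links low levels to dose escalation.

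For the same reasons a compulsory 10 µM gate for Phase II would be a reviewer's preference, not something that follows from the plan.

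It is also fair that CNS antifungal efficacy is given as a second justification, that this is a small descriptive Phase 0 study, and that the primary endpoint (dialysate AUC over 24 hours, Sections 1.2 and 8.3) does not depend on the cut-off. These points limit the severity. They do not settle what may be claimed for a 5 to 10 µM result.

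**Conclusion.** The point holds in a limited form. A success metric is justified partly by a 50% cell-kill range that the text does not give, and the only quoted IC50, from the same report, is twice the cut-off. On that figure the concentration metric can be met at 0.5 × IC50, where predicted kill is below 50% at any positive Hill slope.

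The ratio rests only on the documents. The kill percentages rest on assumed slopes, a 100% maximum effect, and the 10 µM value applying to the line concerned. The pass probabilities rest on assumed medians, CVs and a log-normal shape. Whether 5 µM falls inside the true range across cell lines cannot be decided from the text.

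Severity: should-fix, with moderate confidence.

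**What to change.** In Section 8.2, before any tumour concentrations are known:

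1. Reconcile the justification with Section 2.2. Cite posaconazole IC50 values by cell line that include 5 µM. If there are none, delete the 50%-kill claim and describe at least 5 µM as a penetration criterion set at half the quoted IC50.
2. Report, beside the count at 5 µM, the number of patients at or above the quoted IC50 of 10 µM. This is an added description, not a new gate.
3. State which tumour concentrations count as the lower range that points to dose-escalation studies, and which count as substantial penetration that, with the biological effect, points to Phase II.

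Items 1 and 2 cost wording and one extra line in a table. Item 3 asks the investigators to settle an interpretation now open. No new samples, assays or patients are needed. The downside is that a result between 5 and 10 µM will support a less favourable claim.
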